6.4 Treatment blinding

This is an open-label study and study treatment is not blinded, thus treatments will be known to participants, investigator staff, including persons performing the study assessments.

6.5 Dose escalation and dose modification

Dose interruptions for the investigational study medication (inclisiran) are not permitted.

If a planned dose is missed by less than 3 months, administer inclisiran and maintain dosing according to the participant's original schedule. If a planned dose is missed by more than 3 months, start a new dosing schedule - administer inclisiran initially, again at 3 months, and followed by dosing, thereafter, every 6 months.

Dose interruptions must be recorded on the inclisiran Dose Administration case report form for the investigational study drug.

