6.5.1 Dose modifications

Study drug administration of inclisiran [inclisiran (KJX839), 284 mg liquid in PFS, 1.5 ml] should be temporarily interrupted or permanently discontinued in participants with:

- 1. Intolerable AEs, or if the investigator believes that continuing dosing will be detrimental to the participant's mental or physical health. This includes severe or serious reactions at the injection site and any anaphylactic type reactions.
- 2. Liver laboratory values meeting the study drug interruption criteria listed in Table 16-4 and Table 16-5.

3. Unexplained creatine kinase (CK) values >5 x ULN confirmed by repeat test when the CK elevation is associated with muscle pain, muscle tenderness and/or muscle weakness, or new onset renal dysfunction.

Study treatment may be restarted at the discretion of the investigator, if the reason for discontinuation has resolved.

The dose interruptions must be recorded on an appropriate eCRF.

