16.2 Appendix 2: Liver event and laboratory trigger definitions & follow-up requirements

Table 16-3 Liver event and laboratory trigger definitions

	Definition/ threshold	
Liver laboratory triggers	ALT or AST > 5 × ULN	
If ALT, AST and total bilirubin normal at baseline:	ALP > 2 × ULN (in the absence of known bone pathology)	
	Total bilirubin > 3 × ULN (in the absence of known Gilbert syndrome)	
	ALT or AST > 3 × ULN and INR > 1.5	
	 Potential Hy's Law cases (defined as ALT or AST > 3 × ULN and Total bilirubin > 2 × ULN [mainly conjugated fraction] without notable increase in ALP to > 2 × ULN) 	
	Any clinical event of jaundice (or equivalent term)	
	ALT or AST > 3 × ULN accompanied by (general) malaise, fatigue, abdominal pain, nausea, or vomiting, or rash with eosinophilia	
	Any adverse event potentially indicative of a liver toxicity*	
If ALT or AST abnormal at baseline:	ALT or AST > 2x baseline or > 300 U/L (whichever occurs first)	

^{*}These events cover the following: hepatic failure, fibrosis and cirrhosis, and other liver damage-related conditions; non-infectious hepatitis; benign, malignant and unspecified liver neoplasms ULN: upper limit of normal

Table 16-4 Follow up requirements for liver laboratory triggers with liver symptoms

ALT or AST	TBL	Liver Symptoms	Action
ALT or AST increase v	vithout bilirubin increase) :	
If normal at baseline: ALT or AST > 3 x ULN	Normal For patients with		No change to study treatment
	Gilbert's syndrome: No change in baseline		Measure ALT,
If elevated at baseline:	TBL		AST, ALP, GGT, TBL, direct and
ALT or AST > 2 x baseline		None	indirect bilirubin, PT/INR, albumin, CK, and
or > 300 U/L (whichever occurs			GLDH in 48-72 hours.
first)			Follow-up for symptoms.

ALT or AST	TBL	Liver Symptoms	Action
If normal at baseline: ALT or AST > 5 x ULN for more than two weeks If elevated at baseline: ALT or AST > 3 x baseline or > 300 U/L (whichever occurs first) for more than two weeks	Normal For patients with Gilbert's syndrome: No change in baseline TBL	None	 Interrupt study drug Measure ALT, AST, ALP, GGT, TBL, direct and indirect
If normal at baseline: ALT or AST > 8 x ULN	Normal	None	bilirubin, PT/INR, albumin, CK, and GLDH in 48-72
ALT or AST increase with bilirubin increase:			hours.
If normal at baseline: ALT or AST > 3 x ULN	TBL > 2 x ULN (or INR > 1.5) For patients with		Follow-up for symptoms.

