If elevated at baseline: ALT or AST > 2 x baseline or > 300 U/L (whichever occurs first)	Gilbert's syndrome: Doubling of direct bilirubin	None	 Initiate close monitoring and workup for competing etiologies. Study drug can be restarted only if
If normal at baseline: ALT or AST > 3 x ULN			another etiology is identified and liver enzymes return to
If elevated at baseline: ALT or AST > 2 x baseline or > 300 U/L (whichever occurs first)	Normal or elevated	Severe fatigue, nausea, vomiting, right upper quadrant pain	baseline.

Table 16-5 Follow up requirements for liver laboratory triggers

Criteria	Actions required	Follow-up monitoring
Total Bilirubin (isolated)		
>1.5 – 3.0 ULN	Maintain treatmentRepeat LFTs within 48-72 hours	Monitor LFTs weekly until resolution ^a to ≤ Grade 1 or to baseline
> 3 - 10 × ULN (in the absence of known Gilbert syndrome)	 Interrupt treatment Repeat LFT within 48-72 hours 	Monitor LFTs weekly until resolution ^a to ≤ Grade 1 or to baseline (ALT, AST, total bilirubin, Albumin, PT/INR, ALP and GGT)

Criteria	Actions required	Follow-up monitoring
	Hospitalize if clinically appropriate	Test for hemolysis (e.g., reticulocytes, haptoglobin, unconjugated [indirect]
	Establish causality	unconjugated [indirect] bilirubin)
	Record the AE and contributing factors (e.g., conmeds, med hx, lab) in the appropriate CRF	,
> 10 x ULN	Discontinue the study treatment immediately	ALT, AST, total bilirubin, Albumin, PT/INR, ALP and
	Hospitalize the participant	GGT until resolution ^c (frequency at investigator
	Establish causality	discretion)
	Record the AE and contributing factors(e.g., conmeds, med hx, lab) in the appropriate CRF	
Any AE potentially indicative of a liver toxicity*	Consider study treatment interruption or discontinuation	Investigator discretion
	Hospitalization if clinically appropriate	
	Establish causality	
	Record the AE and contributing factors(e.g., conmeds, med hx, lab) in the appropriate CRF	

^aResolution is defined as an outcome of one of the following: (1) return to baseline values, (2) stable values at three subsequent monitoring visits at least 2 weeks apart, (3) remain at elevated level after a maximum of 6 months, (4) liver transplantation, and (5) death.

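### Section 6.5 bars inclisiran interruptions without exception, which contradicts the safety interruptions directed by Section 6.5.1 and Tables 16-4 and 16-5

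*Protocol*

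**What the plan says.** Protocol Section 6.5 begins: "Dose interruptions for the investigational study medication (inclisiran) are not permitted". It states no exception and does not refer to its own subsection. A missed-dose rule follows, with two branches. For a shorter delay: "If a planned dose is missed by less than 3 months, administer inclisiran and maintain dosing" on the existing schedule. For a delay of more than three months: "start a new dosing schedule - administer inclisiran initially", then a dose at three months and six-monthly dosing. The section ends with a recording duty: "Dose interruptions must be recorded on the inclisiran Dose Administration case report form for the investigational study drug".

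Section 6.5.1 says inclisiran "should be temporarily interrupted or permanently discontinued in participants with" any of three groups of findings: intolerable adverse events or investigator concern about harm, liver values meeting the interruption criteria of Tables 16-4 and 16-5, and confirmed unexplained CK above 5 x ULN with muscle symptoms or new renal dysfunction. It then allows resumption: "Study treatment may be restarted at the discretion of the investigator, if the reason for discontinuation has resolved".

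In Appendix 2, Table 16-4 gives the action "Interrupt study drug" for its more severe ALT/AST rows. It adds "Study drug can be restarted only if" a different cause has been found and the enzymes are back at baseline. Table 16-5 directs interruption for isolated total bilirubin above 3 and up to 10 x ULN, and immediate discontinuation above 10 x ULN. It has no restart sentence. In Appendix 3, Table 16-6 asks the site to consider interruption for a serum creatinine rise of 50% or more and for marked new proteinuria.

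**The concern.** A site handling a safety trigger has two operative dosing instructions. The general one forbids interrupting inclisiran, and the specific one tells the site to interrupt. Section 4.5 relies on dose modification and stopping rules to limit participant risk, so those rules should agree with each other. Section 14 asks investigators to avoid protocol deviations. Read literally, a correct safety hold breaches 6.5, and omitting the hold goes against 6.5.1.

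The missed-dose rule leaves a smaller gap. It says what to do once a planned dose is late but not why the dose was late. A missed appointment and an unresolved liver hold therefore meet the same unconditional text.

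**Working it through.** No formula applies to the main point, so the texts are set side by side.

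**1. Ban against directed interruption**

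- Section 6.5: interruption not permitted, no exception.
- Section 6.5.1: interruption or discontinuation should occur for three groups of findings.
- Table 16-4: interrupt for the more severe ALT/AST rows. The mildest row leaves treatment unchanged.
- Table 16-5: interrupt for isolated bilirubin above 3 and up to 10 x ULN.
- Table 16-6: consider interruption for the renal findings above.

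**2. Which sentence is out of line**

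Section 6.5 itself requires interruptions to be recorded. Section 8.4.1 speaks of stopping study drug temporarily or permanently because of a laboratory abnormality. Section 10.1.1 lists interruption among the actions after an adverse event. Section 10.2.1 provides for considering interruption once a liver elevation is confirmed. Every other provision treats a safety hold as available, so the ban is the sentence to change.

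**3. Worked case**

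Take a participant with normal baseline liver values and no liver symptoms. When the Day 90 dose is due, ALT is known to be above 8 x ULN with normal bilirubin, and no other cause is found. Table 16-4, made operative by 6.5.1, requires interruption, and its restart condition is not met. Section 6.5 forbids the interruption. A site cannot comply with both texts as written.

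**4. The missed-dose rule**

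Both branches say to administer inclisiran, and neither mentions a restart condition. Section 6.5.1 and Table 16-4 do set restart conditions, and Table 16-5 sets none. This is an omission: 6.5 does not say that a held dose counts as a missed one.

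**5. Where that omission can arise**

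Inputs: doses on Days 0, 90 and 270 (Section 4.2), end of study at Day 330 (Table 8-1), visit window of 7 days either side (Section 8). Three months is taken as 90 to 92 days, which is an assumption.

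- Day 270 dose held: 330 - 270 = 60 days remain, at most 60 + 7 + 7 = 74. This is below 90, so only the shorter-delay branch can arise in the study.
- Day 90 dose held: 330 - 90 = 240 days remain, so both branches can arise. The changeover falls at 90 + 90 = Day 180 to 90 + 92 = Day 182.

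These figures show which branch is reachable. They do not measure how often the problem occurs. Doses are 90 and 180 days apart, so a hold that begins and resolves between doses delays nothing.

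**The case against.** The best answer is that 6.5.1 sits directly under 6.5 and is naturally read as its exception. A specific safety list normally prevails over a general sentence, and sites would very probably apply it that way. Section 9.1.1 requires inclisiran to be stopped in any situation where taking part might put the participant at risk. Section 14.1 expects immediate safety action even when it departs from the protocol. These provisions make dosing during an unresolved hold unlikely, and that part of the answer stands. They do not make the sentence in 6.5 correct, since neither 6.5 nor 6.5.1 says that one is an exception to the other.

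A reader might go further and infer that the missed-dose rule orders a catch-up dose during an unresolved safety hold. The documents do not support that. Section 6.5 uses interrupted and missed as separate terms and never equates them. Its missed-dose text works as a scheduling rule, and the next subsection says when held drug may resume. A reader might also say that 6.5 conflicts with restart text in Table 16-5, but that table has none.

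**Conclusion.** The contradiction between the ban in 6.5 and the interruptions directed by 6.5.1 and Tables 16-4 and 16-5 is real. It is a minor safety instruction that is wrong as written. The missed-dose rule is incomplete but not contradictory.

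No count of affected participants is possible, because the documents give no rate for any trigger. It would also be wrong to infer an effect on the primary results. The primary estimands already disregard treatment discontinuation, and the Full Analysis Set keeps every randomized participant, so alpha, power and that analysis do not change.

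One assumption is involved. The restart sentence in Table 16-4 is split across cells in the text available, and it is read here as applying to that table's interrupt rows. The conflict between 6.5 and 6.5.1 does not depend on that reading. The correction has practical value only while inclisiran doses remain to be given.

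**What to change.** Change the opening sentence of 6.5 to: *Dose interruptions are not permitted except for safety reasons as specified in Section 6.5.1 and Appendices 2 and 3.* Citing both appendices matters, because naming only the liver tables would leave the renal provision in Table 16-6 outside the exception unless it fits the general first item of 6.5.1.

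Add before the missed-dose rule: *For a dose held for safety, the missed-dose instructions apply only after restart is allowed under Section 6.5.1 and, for holds under Table 16-4, the restart condition in that table.* Limiting the last part to Table 16-4 avoids imposing an enzyme-based condition on isolated-bilirubin holds under Table 16-5, which sets no such condition.

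The cost is one clause and one sentence, made through a protocol amendment. Data collection, sample size and analyses stay as they are.

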6.5.1 Dose modifications

Study drug administration of inclisiran [inclisiran (KJX839), 284 mg liquid in PFS, 1.5 ml] should be temporarily interrupted or permanently discontinued in participants with:

- 1. Intolerable AEs, or if the investigator believes that continuing dosing will be detrimental to the participant's mental or physical health. This includes severe or serious reactions at the injection site and any anaphylactic type reactions.
- 2. Liver laboratory values meeting the study drug interruption criteria listed in Table 16-4 and Table 16-5.

3. Unexplained creatine kinase (CK) values >5 x ULN confirmed by repeat test when the CK elevation is associated with muscle pain, muscle tenderness and/or muscle weakness, or new onset renal dysfunction.

Study treatment may be restarted at the discretion of the investigator, if the reason for discontinuation has resolved.

The dose interruptions must be recorded on an appropriate eCRF.

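### After a Table 16-4 liver hold, Section 6.5.1 lets the investigator restart inclisiran once the event has resolved, while Table 16-4 also requires another cause to be identified

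*Protocol*

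**What the plan says.** Protocol Section 6.5.1 says that inclisiran "should be temporarily interrupted or permanently discontinued in participants with" any of three conditions: intolerable adverse events, liver values meeting the interruption criteria of Tables 16-4 and 16-5, or unexplained, confirmed CK elevation with muscle symptoms or new renal dysfunction. One restart sentence then covers all three: "Study treatment may be restarted at the discretion of the investigator, if the reason for discontinuation has resolved".

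Table 16-4 (Appendix 2) gives its own restart rule for its interruption rows. The cell is broken in the extracted text, but the sense is clear: "Study drug can be restarted only if" "another etiology is identified and liver enzymes return to" baseline. Both conditions must be met.

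Section 10.2.1 refers the reader to Tables 16-4 and 16-5 for the actions that liver events require. Section 6.5.1 refers to the same tables only for the criteria that trigger an interruption.

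Section 6.5 opens with "Dose interruptions for the investigational study medication (inclisiran) are not permitted", gives timing rules for a missed dose, and then adds "Dose interruptions must be recorded on the inclisiran Dose Administration case report form".

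**The concern.** The same hold is governed by two restart rules, and the one in the main body omits the etiology condition. The case that separates them matters for safety. Section 6.5.2.1 treats drug-induced liver injury as a diagnosis of exclusion. It requires cases that meet its laboratory criteria on repeat testing, with no alternative explanation, to be reported as serious adverse events under the term potential treatment-induced liver injury. These are the participants whom Table 16-4 keeps off drug. Once their values have normalised, the restart sentence in Section 6.5.1, read alone, makes another injection a matter of investigator discretion. At stake is the re-exposure of a participant whose liver event was never explained. Estimation and testing are not at stake.

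**Working it through.** No plan figure needs reproducing, so the check sets the rules side by side.

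**Step 1: do the rules cover the same holds?** Yes, for Table 16-4. The liver item of Section 6.5.1 names that table, and its restart sentence makes no exception for liver. Table 16-4 interrupts drug for normal-baseline participants with ALT or AST >5 x ULN for more than two weeks, >8 x ULN, >3 x ULN with total bilirubin >2 x ULN or INR >1.5, or >3 x ULN with listed symptoms. It has parallel rows for some elevated-baseline cases. I read the restart condition as shared by all interruption rows, as the merged Action cell suggests.

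**Step 2: where do the rules differ?** Section 6.5.1 does not define resolved. Assume it means enzymes back at baseline.

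| Other cause found | Enzymes at baseline | Table 16-4 | Section 6.5.1 |
|---|---|---|---|
| yes | yes | restart allowed | restart allowed |
| yes | no | not allowed | not allowed |
| no | yes | **not allowed** | **allowed** |
| no | no | not allowed | not allowed |

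The rules part only in the third row. The rows are logical situations, not frequencies, and say nothing about how many participants fall in each. If resolved were read more loosely than return to baseline, Section 6.5.1 would allow restart in further cases that Table 16-4 excludes.

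**Step 3: does the third row include possible drug injury?** Yes. For participants with normal baseline values, Section 6.5.2.1 uses ALT or AST >3 x ULN with total bilirubin >2 x ULN. Those are the thresholds in Table 16-4's bilirubin-increase row.

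**Step 4: can the situation arise on this schedule?** Table 8-1 has dosing at Days 0, 90 and 270 and limited chemistry at Days 90, 270 and 330. If Day 90 results come back after that day's injection (assumption), the restart decision concerns the Day 270 dose. That is 270 - 90 = 180 days later. With the +/-7 day window at each visit the range is 263 - 97 = 166 to 277 - 83 = 194 days. Values could normalise in that time with the cause still unknown.

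**Step 5: does the same conflict arise for Table 16-5?** No. It interrupts drug for isolated bilirubin >3 to 10 x ULN and sets no restart condition, so Section 6.5.1 stands there unopposed.

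**The case against.** The strongest reply is that the documents largely settle which rule prevails. Section 10.2.1 names Tables 16-4 and 16-5 as the place for required liver actions. A specific restriction in the designated table ordinarily narrows a general permission that also covers adverse events and CK. An investigator must open Table 16-4 to decide whether a hold applies, and the restart condition sits in the same Action column as the hold. Following Table 16-4 satisfies both rules. Section 9.1.1 adds a backstop, since it requires inclisiran to be stopped where continuing might put the participant at risk.

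Much of this stands. It shows that the stricter rule is intended and limits the point to an uncorrected permission in the main text. It does not remove that permission. No sentence states precedence, Section 6.5.1 reads as a complete restart rule, and Section 9.1.1 depends on judgement and contains no etiology condition.

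A reader might also infer a three-way contradiction, because Section 6.5 says "If a planned dose is missed by less than 3 months, administer inclisiran and maintain dosing" and "If a planned dose is missed by more than 3 months, start a new dosing schedule - administer inclisiran initially". The documents do not support reading this as an order to re-dose after a liver hold. The rule speaks of doses that are missed, not withheld; it never mentions safety holds and was probably written for missed visits. Nor does the sentence barring interruptions prevent a safety hold: Section 6.5.1, a subsection of 6.5, says when to interrupt, and Section 6.5 itself requires interruptions to be recorded. Both are editorial matters.

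**Conclusion.** The inconsistency is real but narrow. It concerns holds triggered by Table 16-4, and only the case where enzymes return to baseline with no other cause identified. In that case Section 6.5.1 permits restart and Table 16-4 forbids it. This rests on reading resolved as return to baseline and on the Table 16-4 restart condition applying to all its interruption rows.

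Its size cannot be put as a number of participants, because neither document gives a rate for these liver triggers. A reader might infer extra protocol deviations, Per-Protocol exclusions or an effect on efficacy; the documents give no basis for the first two, and the primary analysis on the Full Analysis Set is not affected. The point should be corrected because it is a participant-safety rule with an evident intended answer and a trivial remedy.

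**What to change.** In Section 6.5.1, keep the restart sentence and add: 'except that after an interruption triggered by Table 16-4 study drug may be restarted only under the conditions in Table 16-4.' Isolated-bilirubin holds under Table 16-5 stay under the existing Section 6.5.1 rule unless the sponsor sets a separate one.

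Optional tidying in Section 6.5: add 'except as specified in Section 6.5.1 and Appendices 2 and 3' to the sentence on interruptions. Also state that, for a dose held for safety, the missed-dose timing applies only after restart is allowed under Section 6.5.1 as amended. That carve-out should not offer Section 6.5.1 and Table 16-4 as alternatives joined by 'or', since this would leave the looser route open.

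The cost is a minor written amendment with IRB/IEC approval under Section 14.1, distributed to up to about 130 sites. The analysis and the sample size do not change.

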6.5.2 Follow-up for toxicities

6.5.2.1 Follow up on potential drug-induced liver injury (DILI) cases

Participants with transaminase increase combined with total bilirubin increase may be indicative of potentially severe DILI, and should be considered as clinically important events and assessed appropriately to establish the diagnosis. The required clinical information, as detailed below, should be sought to obtain the medical diagnosis of the most likely cause of the observed laboratory abnormalities.

The threshold for potential DILI may depend on the participant's baseline AST/ALT and total bilirubin value; participants meeting any of the following criteria will require further follow-up as outlined below:

- For participants with normal ALT and AST and total bilirubin value at baseline: AST or ALT > 3.0 x ULN combined with total bilirubin > 2.0 x ULN
- For participants with elevated AST or ALT or total bilirubin value at baseline: [AST or ALT > 2 x baseline OR [AST or ALT > 300 U/L] whichever occurs first combined with [total bilirubin > 2 x baseline AND > 2.0 x ULN

As DILI is essentially a diagnosis of exclusion, other causes of abnormal liver tests should be considered and their role clarified before DILI is assumed as the cause of liver injury.

A detailed history, including relevant information such as review of ethanol consumption, concomitant medications, herbal remedies, supplement consumption, history of any preexisting liver conditions or risk factors, should be collected.

Laboratory tests should include ALT, AST, total bilirubin, direct and indirect bilirubin, gammaglutamyl transferase (GGT), glutamate dehydrogenase (GLDH), prothrombin time (PT)/International Normalized Ratio (INR), alkaline phosphatase (ALP), albumin, and CK.

Perform relevant examinations (Ultrasound or Magnetic resonance imaging (MRI), Endoscopic retrograde cholangiopancreatography (ERCP)) as appropriate, to rule out an extrahepatic cause of cholestasis. Cholestasis (is defined as an ALP elevation > 2.0 x ULN with R value < 2 in participants without bone metastasis, or elevation of the liver-specific ALP isoenzyme in participants with bone metastasis). Note: The R value is calculated by dividing the ALT by the ALP, using multiples of the ULN for both values. It denotes whether the relative pattern of ALT and/or ALP elevation is due to cholestatic ($R \le 2$), hepatocellular ($R \ge 5$), or mixed (R > 2 and < 5) liver injury. For children, there are caveats to calculating the R-ratio as normal levels of ALP are higher than in adults with standard ranges varying by developmental age. In clinical situations where it is suspected that ALP elevations are from an extrahepatic source, the GGT

Amended Clinical Trial Protocol (v04 Clean)

can be used if available. GGT may be less specific than ALP as a marker of cholestatic injury, since GGT can also be elevated by enzyme induction or by ethanol consumption. It is more sensitive than ALP for detecting bile duct injury (https://livertox.nih.gov/rucam.html).

Table 6-3 provides guidance on specific clinical and diagnostic assessments which can be performed to rule out possible alternative causes of observed liver function test (LFT) abnormalities.

Table 6-3 Guidance on specific clinical and diagnostic assessments which can be performed to rule out possible alternative causes of observed LFT abnormalities

Disease	Assessment		
Hepatitis A, B, C, E	IgM anti-HAV; HBsAg, IgM & IgG anti-HBc, HBV DNA; anti-HCV, HCV RNA, IgM & IgG anti-HEV, HEV RNA		
CMV, HSV, EBV infection	IgM & IgG anti-CMV, IgM & IgG anti-HSV; IgM & IgG anti-EBV		
Autoimmune hepatitis	ANA & ASMA titers, total IgM, IgG, IgE, IgA		
Alcoholic hepatitis	Ethanol history, GGT, MCV, CD-transferrin		
Nonalcoholic steatohepatitis	Ultrasound or MRI		
Hypoxic/ischemic hepatopathy	Medical history: acute or chronic CHF, hypotension, hypoxia, hepatic venous occlusion. Ultrasound or MRI		
Biliary tract disease	Ultrasound or MRI, ERCP as appropriate		
Wilson disease (if <40 yrs old)	Caeruloplasmin		
Hemochromatosis	Ferritin, transferrin		
Alpha-1-antitrypsin deficiency	Alpha-1-antitrypsin		

Other causes should also be considered based upon participants' medical history (hyperthyroidism / thyrotoxic hepatitis – T3, T4, TSH; CVD / ischemic hepatitis – ECG, prior hypotensive episodes; T1D / glycogenic hepatitis).

Following appropriate causality assessments, as outlined above, the causality of the treatment is estimated as "probable" i.e. >50% likely, if it appears greater than all other possible causes of liver injury combined. The term "treatment-induced" indicates probably caused by the treatment, not by something else, and only such a case can be considered a DILI case and should be reported as an SAE.

All cases confirmed on repeat testing meeting the laboratory criteria defined above, with no other alternative cause for LFT abnormalities identified, should be considered as "medically significant," and thus, meet the definition of SAE and should be reported as SAE using the term "potential treatment-induced liver injury." All events should be followed up with the outcome clearly documented.

